7.2.3 Accountability and Compliance

The Licensed Acupuncturists in this study are licensed in the state of Utah under the Utah Code Title 58 Chapter 72 Acupuncture Licensing Act. Licensed Acupuncturists are also credentialed through the University of Utah medical credentialing department as advance practice clinicians to provide acupuncture treatments in the Huntsman Cancer Hospital and throughout University of Utah healthcare system.

The Licensed Acupuncturists in this study comply with all state and federal regulations for acupuncture and the scope of practice set forth at the Huntsman Cancer Hospital and University of Utah.

7.3 **Prohibited Concomitant Medications**

No concomitant medications are prohibited in this study.

7.4 **Duration of Therapy**

Ten sessions of AT will be delivered: twice per week for 2 weeks, thereafter once per week for six weeks, with a total of 10 treatments during a two-month course. Each session will last 45-60 minutes, with acupuncture needles retained 30-40 minutes. A minimum of 8 treatments must be received by each participant with no more than 10 days' gap between treatments permitted. Participants who do not complete 8 or more acupuncture sessions will be dropped from the study. All participants will be educated as to the importance of completion of the study after baseline.

Subjects must be withdrawn from the study treatment for the following reasons:

- Subject withdraws consent from the study treatment and/or study procedures. A subject must be removed from the trial at his/her own request or at the request of his/her legally acceptable representative. At any time during the trial and without giving reasons, a subject may decline to participate further. The subject will not suffer any disadvantage as a result.
- Subject is lost to follow-up.
- Death.

Subjects may be withdrawn from the study for the following reasons:

- The subject is non-compliant with trial procedures.
- If, in the investigator's opinion, continuation of the trial would be harmful to the subject's well-being.
- The development of an additional cancer.
- Development of an intercurrent illness or situation which would, in the judgment of the investigator, significantly affect assessments of clinical status and trial endpoints.
- Deterioration of ECOG performance status to 4.

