1 OBJECTIVES

This pilot study aims to evaluate the feasibility to conduct a study of acupuncture treatment (AT) for Chemotherapy-Induced Peripheral Neuropathy (CIPN) at Huntsman Cancer Institute and to investigate changes in physiological biomarkers when using acupuncture to treat CIPN.

1.1 **Primary Objectives and Endpoints**

To evaluate the feasibility to conduct a trial of AT for CIPN + standard of care therapy. Primary feasibility objectives will be evaluated in terms of recruitment (enrollment of 20 women, average of 2 eligible women per month to participate in the trial, identification of appropriate recruitment strategies, the appropriateness of eligibility criteria), retention (70% or more participants comply with 8 or more AT sessions and complete both fMRI scans), safety (zero serious adverse events directly related to AT) and questionnaire completion (70% or more enrolled participants comply with all data collection).

1.1.1 Primary outcome measures: Mean enrollment, completion rate of AT, fMRI, rate of serious adverse events, rate of questionnaire completion.

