1.2 Secondary Objectives and Endpoints

To evaluate the impact of AT on the reported experience of CIPN.

- 1.2.1 To evaluate central pain processing and cortical connectivity in patients with CIPN treated by acupuncture by analyzing fMRI of all participants.
- 1.2.2 To evaluate if there is any change in patient-reported measures from before AT to after study completion.

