9 STUDY CALENDAR

			W	eek	(+/·	- 2 d	lays	5)			Week (+/- 7 days)		
Examination	Screenin g ¹	Baseline ^{1,} 2 Day 1	1	2	3	4	5	6	7	8	9	End of study ⁵	22
Informed consent	Χ												
Eligibility criteria	X												
Concomitant medications	X											X	
Questionnaires ³													
• CIPN-20	X											X	X
• BPI		X										X	X
CIPN-R-ODS		X										X	X
• MAIA-2		X										X	X
• Demographics		X											
Acupuncture treatment (AT) ⁴				X X	X X	X	X	X	X	X	X		
fMRI ⁶			X									X	

¹ Screening visit and Baseline visit can occur on the same day.

- ² Day 1 (Baseline) should occur within 2 weeks of the screening visit.
- ³ Questionnaires include: (See Appendices).
- ⁴ Acupuncture treatment (AT) will occur at the Wellness & Integrative Health Center at HCI. Twice a week treatments will occur within 4 business days.
- ⁵ End of study visit should occur within one week of final acupuncture treatment.
- ⁶ Must be within 9 days of baseline visit. If participant prefers, first study fMRI can be same day as first AT treatment.

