Clinical data including current medications and medical history and fall rates will be gathered. Questionnaires (BPI, CIPN-20, CIPN-R-ODS, MAIA-2, Demograhpics) will be completed in person or emailed to patients via REDCap. Reminder calls and AT appointments will be scheduled by HCI Wellness and Integrative Health Center personnel in conjunction with a SC. The SC will aid participants in scheduling fMRI appointments online. AT treatments will occur within 7 days/4 business days in general. If participant prefers the first study fMRI and first AT appointment can occur same day, with the fMRI procedure occurring prior to AT treatment.

Follow up Visits:

Participants will receive 10 sessions of AT: twice per week for 2 weeks, thereafter once per week for six weeks, with a total of 10 treatments during a two-month course. Each session will last 45-60 minutes, with acupuncture needles retained 30-40 minutes. A minimum of 8 treatments must be received by each participant with no more than 9 days' gap between weekly treatments permitted (sessions 5-10). Concurrent medications are allowed as prescribed and will be tracked in the study and analyzed as potential confounders.

Final Visit:

Participants will undergo examination within one week of AT completion. This will include the fMRI scan and questionnaires. Compensation for participation will be offered at this visit.

Procedures:

Measures: Questionnaires will be completed in person or emailed to patients via REDCap at baseline and study conclusion, as well as at a 3-month follow-up. *Primary Endpoints:* Mean enrollment, percentage completion rate of all study procedures, frequency count of serious adverse events, and percentage of enrolled participants completing questionnaires will be calculated. Data will be collected via REDCap, stored in the Research Subject Registry (RSR) and analyzed with SPSS.

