12 STATISTICAL CONSIDERATIONS

Data will be collected via REDCap and analyzed with SPSS. Missing data will be handled with imputation of the median value of all available data for each individual item.¹⁹

Demographics: Analysis of demographic data will consist of calculating means, standard deviations, frequencies, and proportions. Demographic information to include: age, marital status, race and ethnicity, current medications and medical history.

Feasibility data: will be analyzed by calculating frequency and percentages, specifically:

- **Recruitment** frequency count (enrollment of 20 women, average of 2 eligible women per month to participate in the trial, identification of appropriate recruitment strategies, the appropriateness of eligibility criteria),
- **Retention** frequency and percentage (70% or more participants comply with 8 or more AT sessions and complete both fMRI scans)
- Safety frequency count (zero serious adverse events directly related to AT)
- **Questionnaire completion** frequency and percentage (70% or more enrolled participants complete at least 80% of questions at all protocol-directed time points).

Questionnaires: analyses will consist of student t-test and chi square computations according to the type of data.

- CIPN-20
- CIPN-R-ODS
- BPI
- Multidimensional Assessment of Interoceptive Awareness (MAIA-2)

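### Dropping women with fewer than 8 sessions from the study ties questionnaire completion to session adherence and limits observed post-treatment data to adherent women

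*Combined protocol and SAP*

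**What the plan says.** Section 7.4 plans ten sessions, sets a minimum of 8, and says of women below that: "Participants who do not complete 8 or more acupuncture sessions will be dropped from the study". The same section has a separate list of reasons for which a subject may, at discretion, be withdrawn; non-compliance with trial procedures is on it.

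Questionnaires are due at baseline, at study conclusion and at a 3-month follow-up (week 22 in the section 9 calendar). The calendar ties the second of these to treatment: "End of study visit should occur within one week of final acupuncture treatment". Section 10 says of the Final Visit: "This will include the fMRI scan and questionnaires". No section describes later assessments for a woman who has been dropped.

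Two primary feasibility criteria carry a 70% threshold:

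- Retention (section 1.1): "retention (70% or more participants comply with 8 or more AT sessions and complete both fMRI scans".
- Questionnaire completion, worded in three ways. Section 1.1: "70% or more enrolled participants comply with all data collection". Section 12: "70% or more enrolled participants complete at least 80% of questions at all protocol-directed time points". Section 11.1 asks only that enrolled participants comply with data collection, without saying how much or when.

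Secondary objective 1.2.1 looks at central pain processing "in patients with CIPN treated by acupuncture by analyzing fMRI of all participants". The missing-data rule in section 12 is: "Missing data will be handled with imputation of the median value of all available data for each individual item".

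**The concern.** The plan lists retention and questionnaire completion as separate evidence on feasibility. If missing sessions also ends a woman's assessments, one shortfall counts against both criteria, and the questionnaire criterion partly re-measures session adherence. A woman who stops acupuncture but would still have filled in an emailed form is recorded as a data-collection failure.

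The secondary pre/post results would also describe a selected subset, while the plan names no analysis set and objective 1.2.1 speaks of all participants. The pilot is meant to prepare a randomised trial, in which collecting outcomes from women who stop treatment is a practical issue. Under this rule the pilot observes nothing about it.

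**Working it through.** **Inputs from the documents.** Enrolled: 20 (section 4.3, set by budget, with no power calculation to reproduce). Sessions: 2 × 2 + 6 = 10. Threshold: 0.70 × 20 = 14 women.

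**The cap.** Let A be the number of women with 8 or more sessions and Q the number meeting the questionnaire criterion. Two of the three questionnaire time points follow the course of treatment. If a dropped woman is not assessed at those points, she cannot meet the section 1.1 or section 12 wording. Hence Q ≤ A.

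| Dropped | A | Maximum completion | Needed among the A women |
|---|---|---|---|
| 4 | 16 | 80% | 14/16 = 87.5% |
| 5 | 15 | 75% | 14/15 = 93.3% |
| 6 | 14 | 70% | 14/14 = 100% |
| 7 | 13 | 65% | not reachable |

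This step uses no assumed rates, but it does rest on the literal wording of sections 1.1 and 12.

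**Illustration.** The documents give no completion or response rates, so these are assumptions: c = completion among women with 8 or more sessions; q = response among the d others if they were still followed.

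- Under the rule: P(Bin(20−d, c) ≥ 14).
- With follow-up: P(Bin(20−d, c) + Bin(d, q) ≥ 14).

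For example, with d = 6 and c = 0.90 the rule gives 0.90^14 = 0.229. With d = 5 it gives 0.90^15 + 15 × 0.10 × 0.90^14 = 0.206 + 0.343 = 0.549.

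| d | Rule, c = 0.90 | Follow-up, q = 0.50 | q = 0.25 | q = 0.10 |
|---|---|---|---|---|
| 4 | 0.79 | 0.96 | 0.90 | 0.84 |
| 5 | 0.55 | 0.94 | 0.80 | 0.67 |
| 6 | 0.23 | 0.90 | 0.66 | 0.43 |

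At c = 0.95 the rule gives 0.96, 0.83 and 0.49, against 0.99 or more, 0.99 and 0.97 at q = 0.50.

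**Meeting both 70% criteria together.** With p = session adherence and s = completion of both scans among adherent women, and assuming independence, the joint probability is the sum over A = 14 to 20 of P(A) × P(Bin(A, s) ≥ 14) × P(Bin(A, c) + Bin(20−A, q) ≥ 14), with q = 0 under the rule. At q = 0.50:

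- p = 0.75, s = 0.90, c = 0.90: 0.39 against 0.49.
- p = 0.75, s = 0.95, c = 0.85: 0.35 against 0.57.
- p = 0.80, s = 0.95, c = 0.80: 0.37 against 0.64, a gain of 0.27.
- If every woman with both scans also completes all questionnaires (scan and end-of-study forms share the Final Visit), meeting retention guarantees 14 compliers and the gain is 0.

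**Imputation.** Post-treatment item medians would be computed only from women with 8 or more sessions. Filling in the others from those medians does not undo the selection.

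**The case against.** Several counter-arguments have force.

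- **The cap depends on wording.** Section 11.1 does not require all data or all time points. One could also argue that once a woman is dropped, later time points are no longer protocol-directed for her. This stands: the cap follows from the literal text of sections 1.1 and 12, and the three wordings need aligning.
- **The 65% case adds nothing by itself.** With 7 dropped, retention has failed as well, because it needs the same 8 sessions. With 6 or fewer dropped, the rule alone never puts the questionnaire criterion out of reach. A reader might infer that the rule makes the pilot fail; the documents do not support that.
- **There is no joint success rule.** Section 12 reports each criterion as a frequency and percentage. The joint figures above therefore test a decision the plan does not make, and their spread reflects the rates chosen.
- **Few women would be gained.** With 2 of 4 non-adherent women responding, the exact 95% interval is 7% to 93%; with 3 of 6 it is 12% to 88%. That is descriptive information, not a planning rate.
- **A minimum-course mechanism analysis is defensible**, and objective 1.2.1 refers to patients treated by acupuncture. This stands for fMRI, provided the set is named.
- **A specific rule may sit beside a general discretionary list.** That is possible, but the text does not say which governs a woman who misses sessions.

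None of this supplies a provision for assessing dropped women.

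**Conclusion.** The point holds in limited form, as a cheap improvement. As written, women with fewer than 8 sessions leave the study, so questionnaire completion cannot exceed session adherence under the wording of sections 1.1 and 12, and observed post-treatment questionnaires and scans come only from adherent women. On the assumed rates, the chance of meeting the questionnaire criterion could differ substantially when 4 to 6 women are dropped. No overall effect on pilot success is claimed: the joint gain runs from 0 to above 0.25 depending on assumptions.

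Two stronger readings should be resisted. The pre/post results cannot be called biased in acupuncture's favour, because the documents give nothing on the size or direction of any difference between adherent and non-adherent women. Nor is completion bounded by the full retention endpoint: a woman with 8 sessions who misses a scan can still complete every questionnaire.

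**What to change.** In section 7.4, replace the dropping sentence with text such as: *Women with fewer than 8 sessions will be counted as not retained. Unless the woman withdraws consent for assessments, or the investigator withdraws her from the study for a reason listed in 7.4 other than missed sessions, end-of-study and week-22 questionnaires are still collected on the planned calendar, emailed through REDCap if needed.* The calendar places the last session in week 9, so the end-of-study forms fall at about week 10.

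In addition:

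- Use one questionnaire-completion definition in sections 1.1, 11.1 and 12, with all enrolled women as denominator for both 70% criteria. Do not count imputed answers as completed.
- Report completion overall and by session adherence.
- Report pre/post questionnaire changes for all enrolled women with observed data, alongside the subset with 8 or more sessions.
- Name the fMRI analysis set. The set with 8 or more sessions may remain the main one. A second scan for the other women is optional and for the sponsor to decide; report any such scans separately, because their timing relative to the last session differs.
- Reconcile the mandatory session rule with the discretionary withdrawal list. Whether treatment continues is left to the sponsor.

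The cost is a short amendment and a few more contacts. Response among non-adherent women may be low.

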All of these abbreviations may or may not be used in protocol.

PROTOCOL SIGNATURE

I confirm that I have read this protocol, and I will conduct the study as outlined herein and according to the ethical principles stated in the latest version of the Declaration of Helsinki, the applicable ICH guidelines for good clinical practice, and the applicable laws and regulations of the federal government.

I will provide copies of the protocol and all pertinent information to all individuals responsible to me who assist in the conduct of this study. I will discuss this material with them to ensure that they are fully informed regarding the study treatment, the conduct of the study, and the obligations of confidentiality.

Signature of Principal Investigator

12/3/2019 Date

[name] PhD, MAcOM, LAc Principal Investigator Name

College of Nursing, University of Utah Name of Institution

STUDY SUMMARY

Title	Acupuncture Treatment of Chemotherapy-
	Induced Peripheral Neuropathy (CIPN) in
	Women with Breast or Gynecologic
	Cancers: Feasibility and Mechanisms of
	Action
Short Title	CIPN Acu
Protocol Number	N/A
Phase	Clinical study phase: pilot phase II study
Design	Single arm, pilot feasibility study
Study Duration	18 months
Study Center(s)	Single-center: HCI/HCH
Objectives	This pilot study aims to demonstrate
	feasibility to recruit, retain and provide the
	study intervention and to identify potential
	mechanisms of action of acupuncture in
	CIPN management.
Number of Subjects	N=20
Diagnosis and Main Eligibility Criteria	This study will enroll female patients who
	have completed paclitaxel or docetaxel
	treatment at least 3 months prior with at
	least one month of altered sensation in feet
	(with or without presence in one or both
	hands) and/or pain with a score of greater
	than or equal to 20 for CIPN on the
	sensory subscale of the CIPN-20.
	Enrollment will be limited to patients with
	breast, ovarian, cervical, endometrial, or
	uterine cancer with CIPN and completed
	paclitaxel or docetaxel treatments.
Statistical Methodology	Primary Endpoints: Mean monthly
	enrollment, percentage completion rate of
	all study procedures, frequency count of
	serious adverse events, and percentage of
	enrolled participants completing
	questionnaires will be calculated. Data
	will be collected via REDCap and
	analyzed with SPSS.
	Analysis of demographic data will consist
	of calculating means standard deviations
	frequencies and proportions. Analysis of

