11 CRITERIA FOR EVALUATION AND ENDPOINT

11.1 Feasibility

To evaluate the feasibility to conduct a trial of AT for CIPN + standard of care therapy. Primary feasibility objectives will be evaluated in terms of recruitment (enrollment of 20, average of 2 eligible women per month to participate in the trial, identification of appropriate recruitment strategies, the appropriateness of eligibility criteria), retention (70% or more participants comply with AT attendance defined as 8 or more of 10 AT sessions, and complete both fMRI scans), safety (zero serious adverse events directly related to AT) and questionnaire completion (70% or more enrolled participants comply with data collection).

Primary outcome measures: Mean enrollment, completion rate of AT and fMRI, rate of serious adverse events, rate of questionnaire completion.

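### Section 7.4 allows withdrawal from the whole study for non-compliance or for an illness expected to affect the endpoints, and nothing in the plan provides for collecting those women's later data

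*Combined protocol and SAP*

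**What the plan says.** Section 7.4 has two lists of withdrawal reasons with different scope. The mandatory list opens "Subjects must be withdrawn from the study treatment for the following reasons". The discretionary list opens "Subjects may be withdrawn from the study for the following reasons". Two entries on the discretionary list matter here:

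- "The subject is non-compliant with trial procedures". No threshold is given and no decision-maker is named.
- "Development of an intercurrent illness or situation which would, in the judgment of the investigator, significantly affect assessments of clinical status and trial endpoints". This one is left to the investigator's judgment.

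The same section has a separate attendance rule: "Participants who do not complete 8 or more acupuncture sessions will be dropped from the study".

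The outcomes affected are these:

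- **Secondary.** Objective 1.2.2 is "To evaluate if there is any change in patient-reported measures from before AT to after study completion". Questionnaires fall at screening or baseline, end of study and week 22 (Section 9), and the second scan is at end of study. The Study Summary sets two-tailed tests at .05.
- **Primary.** Section 11.1 defines "retention (70% or more participants comply with AT attendance defined as 8 or more of 10 AT sessions, and complete both fMRI scans". The questionnaire criterion in Sections 1.1, 11.1 and 12 is instead expressed over *enrolled* participants.

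Section 12 fills missing items with the median of the available data for that item. It defines no analysis population.

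**The concern.** A woman withdrawn from the study on either ground has no stated route to an end-of-study or week-22 assessment. One ground is the expected effect on the endpoints. The other is compliance with trial procedures, which is what the retention and questionnaire criteria measure. If such women drop out of the data, the answer to objective 1.2.2 applies only to women who complied and had no illness or situation judged to disturb the endpoints. Filling their items from the women who stayed does not restore what was lost.

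The attendance rule does not cover this. It has a fixed threshold, whereas these grounds are discretionary and can reach a woman who has had 8 to 10 sessions. Amending the attendance rule alone would leave them in place.

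The primary retention figure is also exposed. If withdrawn women leave its denominator, a failed criterion can be reported as met, and this pilot is meant to support a decision about a randomized trial.

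**Working it through.** **Is later data collection provided for anywhere?** Sections 7.1, 9 and 10 schedule the assessments without mentioning withdrawn women. Section 12 has only the median rule. Section 16.4.1 follows causally related adverse events to resolution or the 3-month follow-up, but that is not endpoint data. So the plan is silent.

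**Pre/post comparison.** The plan gives no effect size, SD or withdrawal rate, and N = 20 is set by budget (Section 4.3), so there is no plan figure to reproduce. What follows is illustration on stated assumptions: 20 women, true mean change zero, change normally distributed with SD 1, and 2 women removed. Removal is of the two lowest on some feature whose correlation with change is ρ.

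Expected shift in the mean of the remaining 18 = ρ × (sum of the two most extreme expected order statistics of 20) / 18 = ρ × (1.87 + 1.41)/18 = ρ × 0.182.

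The chance of a significant improvement was simulated (200,000 replicates, two-sided .05 paired t-test, counting the favourable direction only; nominal 2.5%).

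| ρ | Shift (SD) | False improvement |
|---|---|---|
| 0 | 0 | about 2.5% |
| 0.2 | 0.04 | 3.5% |
| 0.3 | 0.05 | 4.2% |
| 1 (exactly the two worst changers) | 0.18 | about 15% |

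For scale, 20 pairs detect a change of 0.66 SD with 80% power. The ρ = 0.3 shift is about 8% of that (0.05/0.66) and the extreme case about 28% (0.182/0.66).

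Median filling does not help. In the same simulation at ρ = 0.3, giving the two removed women the median change of the other 18 left the shift at 0.05 SD. It raised false improvement from 4.2% to 6.3%, because the filled values shrink the variance. This simplifies the plan's item-level rule.

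**Retention.** The bar is 0.70 × 20 = 14 women if all enrolled are counted. If two withdrawn women leave the denominator, 0.70 × 18 = 12.6, so 13 suffice. Thus 13/20 = 65% fails, while 13/18 = 72% passes. With an assumed true retention of 65%, the exact binomial chance of meeting the criterion is 0.417 with a bar of 14 and 0.601 with a bar of 13.

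**The case against.** **Selection on observed scores.** A reader might infer that outcomes can be removed because of what they would have been. The documents do not support that. Section 9 schedules no questionnaire between baseline and end of study, so nobody could select on measured change during treatment. The illness ground concerns an intercurrent illness or situation, not a poor score. By week 22 the end-of-study scores already exist, and nothing says collected data are deleted. This stands, and it is why the 15% figure is only an upper bound.

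**Direction.** A reader might also infer that the bias must favour acupuncture. The plan does not show that women with intercurrent illness have worse change in neuropathy. Medications are unrestricted (Section 7.3), and a new illness can alter them. The direction is an assumption.

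**Attribution.** It is tempting to say that an unblinded investigator makes both decisions. Lack of masking is only inferred from the design ("Single arm, pilot feasibility study"), and the non-compliance entry names no decision-maker.

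**Drafting.** The contrast between the two lists may be loose wording, since the treatment list's first entry also speaks of removal from the trial. That is fair, but it is a reason to reconcile the lists, and it does not supply the missing provision for follow-up.

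**Primary endpoint.** The questionnaire criterion already counts enrolled women, so a woman withdrawn without the required questionnaires counts as a failure there. For retention, Section 2 speaks of enrolling and retaining twenty, which points to all 20. What stands is narrow: Sections 11.1 and 12 do not state the retention denominator.

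**Scale.** This is a small, unpowered pilot, the clause is permissive, and it bears mainly on secondary outcomes. That limits the weight of the point but does not remove it, because with 20 women two withdrawals are a tenth of the sample.

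**Conclusion.** The concern holds in a limited form. Section 7.4 permits withdrawal from the study on two grounds tied to the endpoints or to compliance, and the plan provides for neither later data collection nor an analysis set. The pre/post result can therefore describe a selected group. With 2 of 20 removed, the plausible shift runs from nothing to about 0.05 SD (false improvement about 4% against 2.5%, at an assumed correlation of 0.3). The 0.18 SD and 15% case needs exactly the two worst changers to be removed. The number removed, the correlation and the direction are all assumptions.

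With one arm, no between-arm comparison is at stake; the effect is selection in the within-group change. For the primary endpoint, the exposure is confined to the unstated retention denominator, where 65% could be reported as 72%.

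**What to change.** 1. **Section 7.4.** For the non-compliance and endpoint-affecting-illness grounds, state that stopping treatment does not end data collection. The end-of-study and week-22 questionnaires, and the second scan where safe and agreed, are still sought unless the woman withdraws consent or the investigator judges continued participation harmful. Reconcile the scope of the two lists, and make the attendance sentence consistent with this provision so that the two do not conflict for a woman with fewer than 8 sessions. Leave the welfare ground and every decision on stopping treatment unchanged.
2. **Section 12.** Keep the collected scores in the main pre/post analysis. Record the date and nature of any intercurrent illness, and report a sensitivity analysis without the affected scores.
3. **Sections 11.1 and 12.** Use all enrolled women as the retention denominator, and count any withdrawal before 8 sessions or before the second scan as not retained.

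The cost is a short amendment. No new visits or procedures are needed, because the questionnaires can already be emailed through REDCap. The downsides are slightly noisier scores from a few ill women and a retention figure that may be less favourable.
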